14.3.13 No Evidence of Progression or Active Disease

No Evidence of Progression or Active Disease (NEPAD) is a composite measure, evolution of NEDA-3, including relapses and different measurements of disability progression and MRI activity.

NEPAD at Month 24 is defined as the composite endpoint of NEDA-3 and the absence of:

CCI [REDACTED]

CCI [REDACTED]

- 20% progression on T25-FW,
- 20% progression on 9HPT,

during the Treatment Period.

20% confirmed T25FW progression

20% confirmed progression on T25FW is defined by an increase of at least 20% from T25FW Baseline that is sustained over a 6-month time Period.

The increase will be defined as sustained when it occurs on two post-Baseline Visits, which are at least 166 days (6 months * 30 -14 days Visit Window) apart and no score at any other Visit including unscheduled Visits in between is less than the defined increase.

The occurrence of a 20% confirmed T25FW progression is defined as:

- Yes: sustained T25FW progression that started during the Treatment Period.
- No: at least 2 post-Baseline T25FW assessments that are 166 (or more) days apart are available and no sustained T25FW progression that started during the Treatment Period.
- Unknown: Otherwise.

Only T25FW assessments with the same assistance devices as at Baseline will be analyzed. T25FW trials which couldn't be finished by the subjects will be imputed with 3 minutes (see Section 14.3.17).

20% confirmed 9HPT progression

20% confirmed progression on 9HPT is defined by an increase of at least 20% from 9HPT Baseline that is sustained over a 6-month time Period.

The increase will be defined as sustained when it occurs on two post-Baseline Visits, which are at least 166 days (6 months * 30 - 14 days Visit Window) apart and no score at any other Visit including unscheduled Visits in between is less than the defined increase.

The occurrence of a 20% confirmed 9HPT progression is defined as:

- Yes: sustained 9HPT progression that started during the Treatment Period.
- No: at least 2 post-Baseline 9HPT assessments that are 166 (or more) days apart and no sustained 9HPT progression that started during the Treatment Period.
- Unknown: Otherwise.

Analysis of NEPAD

NEPAD will be analyzed with a logistic regression with adjusting factors age (in years) and EDSS at Baseline (≤ 3 , >3).

Analysis (Analysis Set)	Derivation	Statistical Analysis Methods	Missing data handling
Tertiary endpoint: NEPAD at 24 months			
Tertiary (FAS)	NEPAD during the Treatment Period	Same as in the Tertiary Analysis of NEDA (Section 14.3.12)	Same as in the Tertiary Analysis of NEDA (Section 14.3.12)
Tertiary (FAS)	Confirmed T25FW progression during the Treatment Period		
Tertiary (FAS)	Confirmed 9HPT progression during the Treatment Period		

14.3.14 Changes in SDMT outcome at the end of 6, 12, 18 and 24 months compared to Baseline

The SDMT (Symbol Digit Modalities Test) presents a series of nine symbols, each paired with a single digit in a key at the top of a standard sheet of paper. An adapted version of the test is presented in the protocol. Subjects are asked to voice the digit associated with each symbol as rapidly as possible for 90 sec. The SDMT score is the number of correct digits over the 90 sec time span.

Minimal decline in cognitive function is defined by:

- Yes: Change from Baseline in SDMT ≥ -4 at the Month 24 Visit
- No: Change from Baseline in SDMT < -4 at the Month 24 Visit
- Missing: Baseline or Month 24 Visit value is not available

The observed results and changes from Baseline in the SDMT and scaled scores of the SDMT will be tabulated by Visit for the FAS (see Section 18.2).

Analysis (Analysis Set)	Derivation	Statistical Analysis Methods	Missing data handling
Tertiary endpoint: Changes in SDMT outcome at the end of 6, 12, 18 and 24 months compared to Baseline			
Tertiary (FAS)	Change from Baseline in SDMT (raw and scaled scores) at Month i Visit, where i= 6, 12, 18 and 24.	Descriptive summary statistics.	
	Minimal Decline in Cognitive Function at Month 24 Visit compared to Baseline	Descriptive summary statistics	Missing values will be included in the denominator and presented as a separate category.

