12.8 Appendix 8: Expanded Disability Status Score (EDSS)

General

- The Evaluating Physician will complete the EDSS.
- The same individual should remain as the Evaluating Physician for each subject, except when exceptional circumstances make this impossible.
- Prior to each neurological assessment, the Evaluating Physician **should not** refer to any previous neurological assessments carried out on that subject.
- The current EDSS will be recorded (i.e., the EDSS as assessed during the visit).
- The EDSS obtained at screening and baseline visits must fall between x - y as defined by protocol inclusion criteria.

EDSS SCORING

- **0.0** Normal neurological exam [all grade 0 in all FS scores*]
- **1.0** No disability, minimal signs in one FS* (i.e., grade 1)
- **1.5** No disability, minimal signs in more than one FS* (more than 1 FS grade 1)
- **2.0** Minimal disability in one FS (one FS grade 2, others 0 or 1)
- **2.5** Minimal disability in 2 FS (2 FS grade 2, others 0 or 1)
- **3.0** Moderate disability in one FS (one FS grade 3, others 0 or 1) or mild disability in 3 or 4 FS (3 or 4 FS grade 2, others 0 or 1) though fully ambulatory
- **3.5** Fully ambulatory but with moderate disability in one FS (one grade 3) and one or 2 FS grade 2; or 2 FS grade 3 (others 0 or 1) or 5 grade 2 (others 0 or 1)
- **4.0** Fully ambulatory without aid, self-sufficient, up and about some 12 hours a day despite relatively severe disability consisting of one FS grade 4 (others 0 or 1), or combination of lesser grades exceeding limits of previous steps; able to walk without aid or rest some 500 meters
- **4.5** Fully ambulatory without aid, up and about much of the day, able to work a full day, may otherwise have some limitation of full activity or require minimal assistance; characterized by relatively severe disability usually consisting of one FS grade 4 (others 0 or 1) or combinations of lesser grades exceeding limits of previous steps; able to walk without aid or rest some 300 meters
- **5.0** Ambulatory without aid or rest for about 200 meters; disability severe enough to impair full daily activities (e.g., to work a full day without special provisions); (Usual FS equivalents are one grade 5 alone, others 0 or 1; or combinations of lesser grades usually exceeding specifications for step 4.0)

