- **5.5** Ambulatory without aid for about 100 meters; disability severe enough to preclude full daily activities; (Usual FS equivalents are one grade 5 alone, others 0 or 1; or combination of lesser grades usually exceeding those for step 4.0)
- **6.0** Intermittent or unilateral constant assistance (cane, crutch, brace) required to walk about 100 meters with or without resting; (Usual FS equivalents are combinations with more than 2 FS grade 3+)
- **6.5** Constant bilateral assistance (canes, crutches, braces) required to walk about 20 meters without resting; (Usual FS equivalents are combinations with more than 2 FS grade 3+)
- **7.0** Unable to walk beyond approximately 5 meters even with aid, essentially restricted to wheelchair; wheels self in standard wheelchair and transfers alone; up and about in wheelchair some 12 hours a day; (Usual FS equivalents are combinations with more than one FS grade 4+; very rarely pyramidal grade 5 alone)
- **7.5** Unable to take more than a few steps; restricted to wheelchair; may need aid in transfer; wheels self but cannot carry on in standard wheelchair a full day; May require motorized wheelchair; (Usual FS equivalents are combinations with more than one FS grade 4+)
- **8.0** Essentially restricted to bed or chair or perambulated in wheelchair, but may be out of bed itself much of the day; retains many self-care functions; generally has effective use of arms; (Usual FS equivalents are combinations, generally grade 4+ in several systems)
- **8.5** Essentially restricted to bed much of day; has some effective use of arms(s); retains some self-care functions; (Usual FS equivalents are combinations, generally 4+ in several systems)
- **9.0** Helpless bed patient; can communicate and eat; (Usual FS equivalents are combinations, mostly grade 4+)
- **9.5** Totally helpless bed patient; unable to communicate effectively or eat/swallow; (Usual FS equivalents are combinations, mostly grade 4+)
- **10.0** Death due to MS

*Excludes cerebral function grade 1

Note 1: EDSS steps 1.0 to 4.5 refer to subjects who are fully ambulatory and the precise step number is defined by the FS score(s). EDSS steps 5.0 to 9.5 are defined by the impairment to ambulation and usual equivalents in FS scores are provided.

Note 2: EDSS should not change by 1.0 step unless there is a change in the same direction of at least one step in at least one FS.

		Expanded Disability Status Score (EDSS)													
		0	1	1.5	2	2.5	3		3.5			4			

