14.3.17 Changes in level of disability as measured by T25FW

T25FW is a quantitative mobility and leg function performance test based on a timed walk over 25 feet (approximately 7.6 meters). Administration time will vary depending upon the ability of the subject. Subjects have to twice walk a trial of 25 feet. The time limit for each trial is 3 minutes. At least one trial has to be completed to calculate the mean time for a Visit. If the subjects couldn't finish a trial, the trial will be scored with 3 minutes. T25FW performed with a different assistance device as compared to what was used at Baseline will be considered as "changed device" and will not be included in the statistical analysis. Details of the T25FW are included in the appendix of the study protocol.

Analysis (Analysis Set)	Derivation	Statistical Analysis Methods	Missing data handling
Tertiary endpoint: Changes in level of disability as measured by T25FW at Month 6, 12, 18, and 24 Visit compared to Baseline			
Tertiary (FAS)	Change from Baseline in mean time of the T25FW to the Month i Visit, where i= 6, 12, 18, and 24.	Mixed-effects linear model for repeated measures, same as in Tertiary Analysis for Change from Baseline in CUA lesion count (see Section 14.3.1)	Same as in Tertiary Analysis for Change from Baseline in CUA lesion count (see Section 14.3.1)

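### SAP 14.3.13 never counts a sustained new walking aid as T25FW progression: such subjects are classed No or drop out as Unknown

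*SAP*

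**What the plan says.** **Progression rule (SAP 14.3.13).** A subject progresses when the walking time is 20% or more above the Baseline time and stays so for six months. The status has three values. *Yes* is defined as "Yes: sustained T25FW progression that started during the Treatment Period". *No* requires that "at least 2 post-Baseline T25FW assessments that are 166 (or more) days apart are available" and that no sustained increase was seen. Everything else is *Unknown*. On walking aids: "Only T25FW assessments with the same assistance devices as at Baseline will be analyzed". A trial the subject could not finish is scored as 3 minutes.

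**Mean change (SAP 14.3.17).** "T25FW performed with a different assistance device as compared to what was used at Baseline" is labelled as a changed device and "will not be included in the statistical analysis". The model is the repeated-measures model of 14.3.1, which leaves post-Baseline gaps unimputed and assumes they are missing at random.

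**Analysis of the status.** The table in 14.3.13 lists confirmed T25FW progression as an analysis in its own right, beside NEPAD. It uses the logistic regression of 14.3.12, from which subjects of unknown status are excluded.

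**Population.** Protocol 5.3.1 admits EDSS up to 5.0. Protocol Appendix 8 describes step 5.0 as "Ambulatory without aid or rest for about 200 meters" and step 6.0 as "Intermittent or unilateral constant assistance (cane, crutch, brace) required to walk about 100 meters". Protocol 7.3.2.4 lets subjects use an assistive device in the test.

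**The concern.** Subjects enter at EDSS steps that the protocol describes as walking without aid. Changes of device during the trial should therefore run mostly one way, toward more help, so the visits that are discarded mostly record deterioration.

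Not comparing times across devices is defensible. The gap is that nothing replaces the discarded information. A subject who tries the walk on the Baseline device and fails gets 3 minutes, which counts as worsening. A subject who takes a cane instead has the visit removed, and the status is then decided on the earlier, better visits or not decided at all.

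At stake are the separate confirmed T25FW progression rate and the mean T25FW change, both of which would look better than they should.

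**Working it through.** **Inputs.** Post-Baseline T25FW at Months 6, 12, 18 and 24 (protocol 7.3.2.4). Visit windows of ±7 days (protocol section 7). Visit months of 30 days (SAP section 9). Confirmation interval of 166 days (SAP 14.3.13).

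**The plan's own figure.** 6 × 30 − 14 = 166 days. The smallest gap between in-window Month 6 and Month 12 visits is (360 − 7) − (180 + 7) = 353 − 187 = 166 days. Two consecutive in-window half-yearly visits therefore always satisfy the interval required for *No*. If the separate ±5-day allowance for the neurological examination is added, the gap can fall to (360 − 12) − (180 + 12) = 156 days, which would turn some *No* results into *Unknown*.

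**Applying the rule.** Assumptions: nominal visit days, no unscheduled visits, no return to the Baseline device, and an excluded assessment does not count as available. I took every pattern of at least 20% worsening at the earlier same-device visits.

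| Aid first used at | Usable visits | Status under the SAP | Status if a device change at two visits ≥166 days apart counts |
|---|---|---|---|
| Month 6 | 0 | Unknown | Yes |
| Month 12 | 1 | Unknown | Yes |
| Month 18 | 2 (Months 6, 12) | No in 3 of 4 patterns; Yes only if both were already ≥20% worse | Yes |
| Month 24 | 3 | No in 5 of 8 patterns; Yes in the 3 with a sustained same-device increase | Unchanged: one visit cannot confirm |

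The pattern counts show how the rule works. They are not probabilities. In 2 of the 5 Month 24 *No* patterns, Month 18 was already at least 20% worse. These would become *Yes* only under a wider rule that lets a new aid confirm earlier slowing.

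**Direction of the bias in the crude rate.** Let n subjects have a known status and P of them progress under the last column. Suppose the SAP turns m of those progressors into *No* and u into *Unknown*.

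- Reported rate = (P − m − u) / (n − u).
- Loss to *No* alone: (P − m)/n, which is below P/n.
- Loss to *Unknown* alone: (P − u)/(n − u) < P/n if and only if nP − nu < nP − Pu, that is, P < n, which holds unless everyone progresses.

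Both routes lower the rate. The adjusted probability from the logistic regression should move the same way.

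**Mean change.** In 14.3.17 a visit is removed because of a device change seen at that same visit. Device status is not in the model, so the model predicts the missing time as if the subject resembled others with similar earlier times. Missing at random is therefore hard to defend, and the mean is likely pulled toward no worsening.

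**NEPAD.** NEPAD contains NEDA-3, which contains six-month confirmed EDSS progression. The required rises are 1.5 from 0, 1.0 from 0.5 to 4.5, and 0.5 from 5.0 upward. A move from 5.0 or less to 6.0 is a rise of at least 1.0 (from 5.0), at least 1.5 (from 4.5 or less) and 6.0 (from 0), so every threshold is met. EDSS is scored at the same four visits, so a subject at 6.0 at Months 18 and 24 already fails NEPAD.

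**The case against.** The strongest reply is that a same-device restriction is an ordinary comparability choice, since an aid can itself shorten the walking time. It adds that EDSS already captures anyone who truly comes to need a cane, and that the endpoint is tertiary, exploratory and single-arm. Most of this stands:

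- Comparability justifies not using the time. It does not justify returning *No*.
- The EDSS backstop is real, but only inside the composite. The separate T25FW progression analysis has none.
- Someone may use an aid over 25 feet without reaching EDSS 6.0. For that subject the backstop fails, but so does the argument from Appendix 8 that the aid marks worsening.
- The primary lesion analysis is untouched.

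A reader might infer that everyone who comes to need an aid is counted as progression-free. The rule does not do that. An aid first used at Month 6 or 12 gives *Unknown*, prior confirmed slowing on the Baseline device gives *Yes*, and an aid first used at Month 24 could not be confirmed as a device change in any case.

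A reader might also infer that these subjects are counted as NEPAD successes. Those with confirmed EDSS progression are not. Some NEPAD components are blacked out, so the net effect there cannot be judged further.

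**Conclusion.** Wrong as written, on a tertiary endpoint, and of low severity. The SAP discards changed-device T25FW assessments and puts nothing in their place, so a sustained new aid never counts as T25FW progression. Absent earlier confirmed slowing on the Baseline device, the subject becomes *No* (aid first used at Month 18 and kept) or *Unknown* and excluded (Month 6 or 12). Both bias the separate progression rate downward, and the mean-change model rests on a doubtful missing-at-random assumption for the same visits.

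The size cannot be derived. Neither document gives a rate of new walking aids or of T25FW progression. It is tempting to divide an assumed rate of new aids by an assumed rate of progression, but that would also count subjects who are already *Yes* and those whose aid first appears at Month 24.

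The conclusion assumes that an excluded assessment is not available for the *No* rule, which the SAP does not state. If it were, early aid users would also become *No*.

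**What to change.** **SAP 14.3.13.** Count a change from no device, or a lesser one, to a greater device as confirmed T25FW progression when it is present at two post-Baseline visits at least 166 days apart. State the ordering of devices; Appendix 8 already separates unilateral from bilateral assistance. State also that an excluded assessment is not available for the *No* category.

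**SAP 14.3.17.** Tabulate changed-device visits by visit. Keep the same-device model and add a sensitivity analysis using the observed times whatever the device. Do not give 3 minutes to walks that were completed. The SAP reserves that score for unfinished trials, and 180 seconds for finished ones would distort a mean from a linear model.

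**Cost.** One rule, one table and one extra model run, settled before final database lock. No new data are needed, because the present rule cannot be applied without the device at each visit. The reported progression rate may rise.

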- Period 100.1 (p_{100.1}) is defined as the Period between Baseline and Month 1 MRI scans,

- Period 100.2 (p_{100.2}) is defined as the Period between Month 1 and Month 2 MRI scans,
- Period 100.3 (p_{100.3}) is defined as the Period between Month 2 and Month 3 MRI scans,
- Period 100.6 (p_{100.6}) is defined as the Period between Month 3 and Month 6 MRI scans,
- Period 100.12 (p_{100.12}) is defined as the Period between Month 6 and Month 12 MRI scans,
- Period 100.15 (p_{100.15}) is defined as the Period between Month 12 and Month 15 MRI scans,
- Period 100.18 (p_{100.18}) is defined as the Period between Month 15 and Month 18 MRI scans,
- Period 100.24 (p_{100.24}) is defined as the Period between Month 18 and Month 24 MRI scans.

Note: Period start and end dates are defined by the MRI dates as provided by central reading.

Definition of change from Baseline

Change from Baseline = Visit value – Baseline value.

Percentage Change from Baseline = $100 \times (\text{Visit value} - \text{Baseline value}) / \text{Baseline value}$.

The Percentage Change from Baseline will be set to missing for subjects with a zero at Baseline.

Definition of Visit dates

The Visit start date is the date of the first assessment which belongs to the corresponding Visit.

The Visit end date is the date of the last assessment which belongs to the corresponding Visit.

Definition of duration

Duration will be calculated by the difference of start and stop date + 1, in days (unless specified otherwise).

Treatment Period

The treatment Period begins with the start of study medication on Study Day 1 and continues through to the completion of the treatment Period at the Month 24 Visit (see CSP, Section 7.1.2). Start of study medication is the date of first intake of study medication. Start of study medication in Year 2 is the date of first intake of study medication at or after the Month 12 Visit.

Treatment Period:

- Start = Start of study medication,
- End = Visit end date of Month 24 Visit, or Early Termination (ET) Visit, in case of early discontinuation, or the study discontinuation date, if the ET Visit was not performed.

Course 1 Treatment Period:

- Start = Start of study medication,

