14.3.8 Responder rate during the different Periods

Subjects will be classified as Responder for a post-Baseline Period if the standardized CUA lesion count decreased by at least 1 in 6 months in comparison to the Baseline Period:

- Responder: $\Delta\text{CUA}(p_i) = (\#\text{CUA}(p_i) - \#\text{CUA}(p_0)) * 6 \geq -1$, $i = \text{Period } 1, 2, 3$,
- Non-Responder: otherwise.

Subjects with missing assessments will be classified as “Non-Responder”.

Analysis (Analysis Set)	Derivation	Statistical Analysis Methods	Missing data handling
Tertiary endpoint: Responder rate during the different post-Baseline Periods ^(a)			
Tertiary (FAS)	Responder rates for Periods 1-3.	Descriptive summary statistics and 95% confidence intervals	Missing Baseline Period: Subjects with a missing CUA lesion count for the Baseline Period will not be included in analysis. Subjects with a missing post-Baseline Period will be classified as Non-Responder for the respective Period.
(a) 6-month interim analysis			

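### SAP 14.3.14: the label for minimal cognitive decline and its SDMT rule do not agree, because Yes also covers subjects who were stable or improved

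*SAP*

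**What the plan says.** SAP 14.3.14 defines a three-way category for the SDMT at Month 24. The lead-in is "Minimal decline in cognitive function is defined by", and three rules come after it:

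- The first sets a floor and no ceiling: "Yes: Change from Baseline in SDMT ≥ -4 at the Month 24 Visit".
- The second takes everything under that floor: "No: Change from Baseline in SDMT < -4 at the Month 24 Visit".
- The third holds subjects who lack one of the two scores: "Missing: Baseline or Month 24 Visit value is not available".

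The table in that section lists the variable as "Minimal Decline in Cognitive Function at Month 24 Visit compared to Baseline". It is summarised descriptively on the FAS, with missing values kept in the denominator as their own category.

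Two other statements fix the direction. SAP 14.3.14 says "The SDMT score is the number of correct digits over the 90 sec time span", so a higher score is better. SAP Section 9 says "Change from Baseline = Visit value – Baseline value", so a decline is negative.

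A neighbouring rule is relevant. SAP 14.3.8 describes a responder as a subject whose standardized CUA count "decreased by at least 1 in 6 months in comparison to the Baseline Period", but the formula beneath requires six times the difference (post-baseline minus baseline) to be ≥ −1.

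**The concern.** A row headed minimal decline should count subjects who declined a little, or perhaps subjects who declined by some minimum amount. The rule counts neither group. Its Yes category has a floor at −4 and no ceiling, and the only alternatives are No (below −4) and Missing. Stable and improved subjects have nowhere to go except Yes.

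Cognition is named in the tertiary objectives (Protocol 4.3). This row is the only categorical SDMT summary in the plan, and no model is planned for SDMT, so a reader looking for one statement about cognitive decline would probably quote it. Followed as written, the row could be quoted as showing decline in people who had none.

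**Working it through.** The documents give no planned figure for this variable, so there is nothing to reproduce. The check applies the written rule to specific values.

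**Inputs.** Change = Month 24 score − baseline score (SAP Section 9). Higher is better (SAP 14.3.14). Yes if change ≥ −4; No if change < −4. Scores are whole numbers, so No means a fall of 5 or more.

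**Rule compared with two literal meanings of the label.**

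| SDMT change | SAP rule | Decline of at least 4 (≤ −4) | Small decline only (−4 to −1) |
|---|---|---|---|
| −15, −10, −5 | No | Yes | No |
| −4 | Yes | Yes | Yes |
| −3, −1 | Yes | No | Yes |
| 0, +1, +4, +10 | Yes | No | No |

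The SAP rule matches neither column. Changes of 0 or more are the values it misplaces under both meanings. The −4 used in the two comparison columns is borrowed from the SAP's own cut-off and is not an independently supported threshold.

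**How large the group might be.** The documents give no mean or SD for SDMT change, so this is an illustration only. Assume a normal distribution with mean m from −2 to +4 and SD s from 5 to 10, with continuity correction, among subjects with both values:

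- Share coded Yes = 1 − Φ((−4.5 − m)/s). Lowest, m = −2 and s = 10: 1 − Φ(−0.25) = 0.599. Highest, m = 4 and s = 5: 1 − Φ(−1.7) = 0.955.
- Share with change ≥ 0 = 1 − Φ((−0.5 − m)/s). For m = −2 and s = 5 this is 0.382, and the Yes share is 0.691, so 0.382/0.691 = 55% of Yes subjects did not decline. For m = 4 and s = 5 it is 0.816/0.955 = 85%.

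Under these assumptions 60% to 96% of evaluable subjects would be Yes, and 55% to 85% of those would not have declined.

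**Responder rule in SAP 14.3.8.** The formula is (post-baseline − baseline) × 6 ≥ −1.

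- Monthly count falls by 1: −1 × 6 = −6, which is not ≥ −1, so Non-Responder.
- Count unchanged: 0 × 6 = 0, which is ≥ −1, so Responder.
- Count rises by 1: 1 × 6 = 6, which is ≥ −1, so Responder.

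The words require a decrease of at least 1, which is (post-baseline − baseline) × 6 ≤ −1. Words and formula agree only at exactly −1.

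**The case against.** The best defence is that the label means at most a minimal decline. On that reading Yes is the favourable outcome, the partition is complete, a fall of 5 or more is correctly No because it is more than minimal, and a high Yes share is the right result. This stands as a possible intent: it makes the rule coherent and leaves only the label at fault. It does not remove the point, because neither the definition nor the table row says so, and a subject who gained 10 points had no decline of any size.

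A reader might infer more: that the inequality is simply reversed. The documents do not establish this.

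- **Coding direction is mixed.** Yes marks the adverse outcome for T25FW and 9HPT progression (SAP 14.3.13) and for brain atrophy (SAP 14.3.11), but the favourable outcome for NEDA-3 (SAP 14.3.12).
- **SAP 14.3.8 is not proof.** There the SAP's own words contradict its formula, so the error is visible within the section. SAP 14.3.14 has no verbal rule for the inequality to contradict, so treating it as the same slip is analogy.

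It is also fair that the stakes are low. Raw and scaled SDMT changes are summarised at Months 6, 12, 18 and 24 in the same section, so the direction of change remains visible.

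**Conclusion.** The label and the rule in SAP 14.3.14 do not agree, and the row would mislead if produced as written. Whether the inequality or the label is wrong cannot be settled from the documents.

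Measured against the label as it stands, the mislabelled group is every subject with a change of 0 or more. Its size is unknown; the percentages above depend wholly on the assumed means and SDs.

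Two further inferences should not be drawn. One is that if 10–20% of subjects fall by 4 or more, the table would show 80–90% with decline. That share is an assumption, the rule codes a fall of exactly 4 as Yes, and missing values stay in the denominator. The other is that a change of exactly −4 belongs with decline. Apart from the disputed rule, the visible documents give no threshold for relevant SDMT decline.

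The impact is limited to one descriptive tertiary row. SDMT is not among the visible components of NEDA or NEPAD, although some NEPAD components are redacted and could not be checked. The primary analysis is not affected.

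The responder contradiction in SAP 14.3.8 is separate and can be shown from that section alone. It affects a tertiary rate reported with 95% confidence intervals at the 6-month interim analysis.

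**What to change.** In SAP 14.3.14, choose one meaning and make the label and rule say it:

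1. If the favourable category is intended, rename it *No more than minimal decline (change ≥ −4)* in the definition and the table row, and keep the rule.
2. If decline is intended, redefine it as *SDMT decline: Yes if the change is at or beyond the stated negative threshold, No otherwise*, with the sponsor stating the threshold and on which side a change of exactly −4 falls.

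In SAP 14.3.8, change the responder condition to ≤ −1 so that it matches the words. SAP Section 7 indicates that the primary analysis had already been performed when this version was written, so the sponsor should also confirm which condition was programmed for the interim responder rates and rerun them if it was ≥ −1.

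The cost is one line and one table label in 14.3.14, one symbol in 14.3.8, and a program check. No data collection changes.
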